Chemistry (Excluding LFTs)	X ^b		X	X	Collect predose; includes assessments for sodium, potassium, chloride, total serum calcium, magnesium, bicarbonate/carbon dioxide, phosphorus, BUN, creatinine, glucose, total protein, albumin, amylase, lipase, uric acid, ferritin, LDH, HDL, and LDL.
CBC with Differential and Platelets	X ^b	X	X	X	Collect predose. In addition, please collect predose on Day 4 (±1) day.

Table 2-2: On-treatment Procedural Outline (BMS-986242 Monotherapy in Part 1 Dose Escalation)

Procedure	Cycle 0				Notes
	Day 1	Day 2	Day 8	Day 14	
LFT Assessments	X ^b		X	X	Includes AST, ALT, total bilirubin, direct bilirubin (only if total bilirubin is elevated), alkaline phosphatase, and GGT (only when alkaline phosphatase is increased to ≥ Grade 2). Collect predose; LFTs should be repeated 4 hours postdose on Cycle 0 Day 14.
Pregnancy Test (WOCBP)	X				Serum or urine pregnancy test must be performed (urine pregnancy test: minimum sensitivity 25 IU/L or equivalent units of hCG) within 24 hours prior to administration of study treatment. If pregnancy test is positive, hold all study treatment and perform confirmatory testing. If pregnancy is confirmed, permanently discontinue all study treatment and immediately notify the Sponsor per Section 9.2.5 .
Concomitant Medication Assessments	X	X	X	X	Review prior to dosing.
Monitor for Nonserious Adverse Events	X	X	X	X	Nonserious AEs will be collected starting with the first dose of study treatment until 100 days after discontinuation of nivolumab.
Monitor for Serious Adverse Events	X	X	X	X	All SAEs must be collected from the date of participant's written consent until 100 days after discontinuation of nivolumab or participation in the study (if the last scheduled visit occurs at a later time). eSAEs should be approved in the BMS EDC tool within 5 business days of entry.
Pharmacokinetic Assessments	See Section 9.5.3 and Table 9.5.3-1 .				Performed in all participants
Immunogenicity Assessments	See Section 9.5.3 , Section 9.8.3 , and Table 9.5.3-1 .				Performed in all participants

Table 2-2: On-treatment Procedural Outline (BMS-986242 Monotherapy in Part 1 Dose Escalation)

Procedure	Cycle 0				Notes
	Day 1	Day 2	Day 8	Day 14	
					
Additional Research	See Section 9.8.2 .				
Study Treatment Administration	Details regarding preparation and administration are provided in the site training materials.				

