3.3 Overall Benefit/Risk Assessment

3.3.1 Risk/Benefit for BMS-986242

There is no prior human experience with BMS-986242; therefore, clinical benefit has not been assessed in participants with advanced cancer. Other IDO1 inhibitors have entered human trials, both as monotherapy and in combination with other anti-cancer treatments (epacadostat from Incyte Corporation, GDC-0919 from Roche, indoximod from NewLink Genetics, and BMS-986205, from Bristol-Myers Squibb). Published safety information for epacadostat shows a favorable safety profile as monotherapy (ie, well tolerated across all dose levels, with the most common AEs being Grade 1 or 2 fatigue and gastrointestinal disturbances)¹⁹, suggesting no intrinsic risk of suggesting no intrinsic risk of severe toxicity with IDO1 blockade. The assessment of potential clinical benefit of BMS-986242 is based upon preclinical human xenograft model SKOV3, in which significant IDO1 inhibition was achieved.

In the absence of clinical studies, the assessment of the risk of side effects of BMS-986242 in clinical trials is based upon data from nonclinical toxicology studies in rats and dogs. In rats, multiple doses up to 10 mg/kg/day were well-tolerated, while single doses \geq 20 mg/kg resulted in overt CNS toxicity. In dogs, the top dose studied exceeded the MTD. Clinical signs included vomiting, diarrhea, dehydration, and weight loss. Chronic inflammation was noted in the gallbladder at 100 mg/kg/day and corresponded with increases in serum GGT and ALT activity. The gallbladder inflammation and serum chemistry changes were reversible. CNS and respiratory safety pharmacology assessments were conducted as part of the pivotal 1-month oral toxicity studies in rats and dogs. There were no BMS-986242-related CNS signs or effects on cranial or spinal nerve function or respiratory function at doses up to 10 mg/kg/day in rats and up to 100 mg/kg/day in dogs.

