The nonclinical toxicity profile was used to determine the human starting dose and to develop appropriate exclusion criteria and safety monitoring for this study. Complete blood counts and chemistry test results (including liver and kidney functions) will be assessed weekly during monotherapy and Cycle 1 of combination and every 4 weeks (Q4W) thereafter. In addition, complete physical examinations (PEs) will be conducted on Day 1 of each cycle, with additional symptom-directed PEs at least weekly during monotherapy and Q2W for the first 12 weeks during combination. Participants with viral hepatitis or other liver disease, such as nonalcoholic fatty liver disease, will be excluded to minimize the potential for hepatotoxicity. Assays for cardiac ion channels did not indicate a potential for cardiovascular liability. Nevertheless, participants with QTc prolongation at baseline will be excluded, medications known to cause prolonged QT will be prohibited, and electrocardiograms (ECGs) will be monitored during the study.

Continuous safety assessments will be utilized by the investigators and Sponsor to determine whether dose modification, additional safety measures, or termination of the study is required at any time. In addition, AEs and serious adverse events (SAEs) will be reviewed on an ongoing basis by the Sponsor's Medical Monitor and Global Pharmacovigilance and Epidemiology representatives to monitor for any safety signals or trends.

As BMS-986242 is an experimental agent, it is possible that unforeseen, unknown, or unanticipated reactions may occur. Based on the nonclinical safety profile of BMS-986242, and with a 60-fold safety margin built into the planned starting dose of 25 mg daily, the potential safety risks are expected to be minimized. Taking a conservative approach, an initial 12.5 mg starting dose will be used (see [Section 5.5.1](#)). A Bayesian Logistic Regression Method (BLRM) with overdose control principle will be employed to ensure that safety is not compromised during dose escalation. This method limits the risk of exposing participants in the next cohort to an unsafe or toxic dose.

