Cohort tolerability assessment and subsequent dose recommendation may occur when 2 DLT-evaluable participants within a cohort have completed the 6-week DLT observation period (see [Section 7.4.1](#) for criteria for DLTs). DLTs occurring within the 2-week lead-in period (DLT observation period for monotherapy) will be used to fit the BLRM model for monotherapy. DLTs occurring within the 4 weeks of combination period (DLT observation period for combination) will be used to fit the BLRM-copula model. If a potential DLT occurring in any third evaluable participant does not influence the dose recommendation by BLRM (-copula), then the BLRM (-copula)-recommended next dose level may proceed without waiting for the third participant to complete the corresponding DLT observation period after discussion and agreement by the sponsor and investigators. The lower recommended dose from both models will be considered for the next dose escalation. Participants receiving $\geq 75\%$ (11 out of 14 doses) of BMS-986242 in the 2-week lead-in cycle will be considered as DLT-evaluable participants for BMS-986242 monotherapy. Participants who receive at least 1 dose of nivolumab and have been followed at least 5 days and receive $\geq 75\%$ BMS-986242 (21 out of 28 doses) in the 4-week DLT observation period for combination therapy will be considered as DLT-evaluable participants. Continuous re-assessment of dose recommendation by BLRM will be carried out at each dose level after each cohort of participants with consideration of all available DLT information. In order to allow additional safety, PK, and pharmacodynamic assessment, in Part 1 up to 12 additional participants may be enrolled at any dose level at or below the MTD, up to a total of 24 additional participants.

No intra-participant dose escalation is allowed, although dose modifications of BMS-986242 may be permitted (see [Table 7.4.2-1](#)).

[figure not shown]
Sentinel Participant: During dose escalation, a staggered dosing (sentinel participant) approach will be used. In the first dose level, the first participant in both lead-in and combination will receive the Cycle 0 Day 1 or Cycle 1 Day 1 dose(s) of study treatment(s) and be observed for 5 days before additional participants in that cohort receive monotherapy or combination study treatment. In subsequent dose levels, a sentinel participant with a 5 day observation period will be used for Cycle 0 Day 1.

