5.1.5 Data Monitoring Committee and Other External Committees

BMS has elected not to use a Data Monitoring Committee for this study. In addition to the comprehensive safety monitoring plan outlined below, the following key points were considered for this decision:

- This is an open-label study.
- The eligibility criteria exclude participants with disease characteristics that could predispose to higher risk of morbidity, eg, uncontrolled or significant cardiovascular disease, etc.
- Exclusion of participants with active, known, or suspected autoimmune disease also applies, as they could be at risk for exacerbation of their condition by the administration of therapies that relieve immune suppression such as BMS-986242 and nivolumab.
- Participants will be observed frequently for clinical evaluation and blood counts during dose escalation.
- Well-defined discontinuation criteria are established in the protocol for individual participants for both safety and treatment futility with clear criteria for treatment discontinuation, dose delay, and toxicity management.

BMS has in place a multi-layered process for ensuring patient safety through close collaboration of study site investigators, the BMS study team, and the BMS GPVE-led Medical Surveillance Team (MST). This collaborative process constitutes the Data Safety Monitoring Plan for the study as detailed below:

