7.4.1.1 Dose-limiting Toxicities

Dose-limiting Toxicities for DLT1 and DLT2 Periods

Nonhematologic DLT:

A. Hepatic, Nonhematologic DLT

Any of the following events will be considered a hepatic DLT:

- Any \geq Grade 3 elevation of AST, ALT, or total bilirubin
- Grade 2 AST or ALT with symptomatic liver inflammation (eg, right upper quadrant tenderness, jaundice, pruritus)
- AST or ALT $> 3 \times$ ULN and concurrent total bilirubin $> 2 \times$ ULN without initial findings of cholestasis (elevated serum alkaline phosphatase; eg, findings consistent with Hy's law or Food and Drug Administration definition of potential drug-induced liver injury [DILI])*

*Note that this special category of DLT uses ULN rather than Common Toxicity Criteria Grade for definition.

B. Nonhepatic, Nonhematologic DLT

Any of the following events will be considered a nonhepatic, nonhematologic DLT:

- Grade 2 or greater episcleritis, uveitis, or iritis
- Any other Grade 2 eye pain or blurred vision that does not respond to topical therapy and does not improve to Grade 1 severity within 2 weeks OR requires systemic treatment
- Any Grade 3 or greater nondermatologic, nonhepatic, nonhematologic toxicity will be considered a DLT with the following specific EXCEPTIONS:
 - Grade 3 or Grade 4 electrolyte abnormalities that are not complicated by associated clinical adverse experiences, last less than 48 hours, and either resolve spontaneously or respond to conventional medical intervention
 - Grade 3 nausea, vomiting, or diarrhea that lasts less than 48 hours and either resolves spontaneously or responds to conventional medical intervention
 - Isolated Grade 3 elevation of amylase or lipase not associated with clinical or radiographic evidence of pancreatitis
 - Isolated Grade 3 fever not associated with hemodynamic compromise (eg, hypotension, clinical or laboratory evidence of impaired end-organ perfusion)
 - Grade 3 endocrinopathy that is well controlled by hormone replacement
 - Grade 3 tumor flare (defined as pain, irritation, or rash that localizes to site of known or suspected tumor)
 - Grade 3 fatigue
 - Grade 3 infusion reaction that returns to Grade 1 in less than 6 hours

C. Dermatologic DLT

- Grade 3 rash if no improvement (ie, resolution to \leq Grade 1) after a 1- to 2-week infusion delay. Participants who have not experienced a Grade 3 study treatment-related skin AE may resume treatment in the presence of Grade 2 skin toxicity.

- Grade 4 rash of any duration.

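### The Cycle 0 sentinel can be cleared on Day 5 or 6 with no on-treatment liver or kidney result, because the first one is scheduled on Day 8

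*Combined protocol and SAP*

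**What the plan says.** Section 5.1.2.1 staggers dosing within each escalation cohort. At the first dose level the first participant, in the lead-in and again in combination, must "be observed for 5 days before additional participants in that cohort receive monotherapy or combination study treatment". For higher levels the text reads: "In subsequent dose levels, a sentinel participant with a 5 day observation period will be used for Cycle 0 Day 1". It names no test that has to be available, and no review that has to take place, before the others are dosed.

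Table 2-2 sets out the Cycle 0 schedule. Chemistry and LFTs are marked on Days 1, 8 and 14. The Day 1 samples are predose, and a footnote lets results up to 72 hours old stand in for them, so they are baseline values. The blood count is marked on Days 1, 2, 8 and 14, and its row alone carries a further instruction: "In addition, please collect predose on Day 4 (±1) day". The LFT row has one addition outside the weekly pattern: "LFTs should be repeated 4 hours postdose on Cycle 0 Day 14".

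Section 3.3.1 gives weekly testing as the intended frequency: "chemistry test results (including liver and kidney functions) will be assessed weekly during monotherapy and Cycle 1 of combination". Section 5.1.5, in explaining why there is no data monitoring committee, says: "Participants will be observed frequently for clinical evaluation and blood counts during dose escalation".

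Section 7.4.1.1 opens the hepatic DLT list with any "Grade 3 elevation of AST, ALT, or total bilirubin" or worse, with no symptom attached.

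**The concern.** A sentinel is useful only for what is known about that participant when the others are cleared to start. Section 3.3.1 says the drug has not been given to humans before. Participants with liver disease are excluded to limit hepatotoxicity, and the hepatic DLT list starts with a pure laboratory threshold. Yet under Table 2-2 the 5 days can pass with no on-treatment ALT, AST, bilirubin or creatinine for the sentinel. Clinical observation alone would not reveal an elevation without symptoms.

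Entry limits leave little headroom for some participants. Section 6.1 admits ALT and AST up to 3 times the upper limit of normal, which is also the transaminase threshold in the combined liver-injury DLT (that criterion additionally requires bilirubin above twice the limit). At stake is whether the remaining participants at a dose level start before the first such result from the person who went first.

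**Working it through.** The plan gives no figure to reproduce. The check is day arithmetic on Section 5.1.2.1 and Table 2-2.

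**Inputs**
- Observation: 5 days from Cycle 0 Day 1 (Section 5.1.2.1).
- Chemistry and LFTs: Day 1 predose, Day 8, Day 14 (Table 2-2).
- Extra blood count: predose on Day 4 (±1), that is Days 3 to 5 (Table 2-2).
- Predicted human half-life: 13 hours (Section 7.4.1).

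**1. End of observation.** Counting Day 1 as the first day: 1 + 5 − 1 = Day 5. Counting 5 full 24-hour periods: 1 + 5 = Day 6.

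**2. Gap to the first on-treatment chemistry and LFTs.** 8 − 6 = 2 days, or 8 − 5 = 3 days. The number of scheduled on-treatment chemistry or LFT results inside the window is 0.

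**3. What the window does contain.** ECGs 2 and 4 hours after the Day 1 dose, PK sampling, a symptom-directed examination on Day 2, adverse event review, and blood counts on Day 2 and Day 4 (±1). The sentinel is observed; what is missing is liver and kidney chemistry.

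**4. Which day of the existing draw would serve.** Days left for a local result = end of observation − draw day.

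| Draw day | Observation ends Day 5 | Observation ends Day 6 |
|---|---|---|
| 3 | 2 | 3 |
| 4 | 1 | 2 |
| 5 | 0 | 1 |

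A Day 5 draw may leave no time for the result, so for the sentinel the window should be Day 3 or Day 4.

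**5. Exposure at that draw.** Fraction of steady state = 1 − 0.5^(t/13), with t in hours since the first dose.
- Day 3 predose, after 2 doses: 1 − 0.5^(48/13) = 0.92.
- Day 4 predose, after 3 doses: 1 − 0.5^(72/13) = 0.98.

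If the predicted half-life holds, an early draw samples close to full exposure. That says nothing about how quickly ALT would respond.

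**6. Visit burden.** The Day 4 (±1) blood count already brings the participant in, and Section 7.6 has the dose taken at the clinic on laboratory days. The added tests need no new visit.

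**The case against.** The strongest reply is that the schedule is deliberate. Section 3.3.1 states weekly chemistry, Table 2-2 carries it out, and early blood counts and one extra LFT were placed test by test. A reader might infer from the gap that the plan contradicts itself or that a test was left out by mistake. The documents do not support that: no two sections conflict, and unscheduled tests are not barred. What remains is that Section 3.3.1 does not address the sentinel's release, and an elevation without symptoms gives no reason to order an unscheduled test.

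The second reply is that the liver rationale for so early a window is thin. The dog finding reads: "Chronic inflammation was noted in the gallbladder at 100 mg/kg/day and corresponded with increases in serum GGT and ALT activity". It was reversible, and the top dose in that species exceeded the tolerated dose. Section 3.3.1 cites a 60-fold margin at 25 mg, and dosing starts at 12.5 mg. The toxicity tied to single doses was neurological, in rats, and the early clinical examinations bear on that. A reader might infer that the dog data predict an ALT rise within days. They do not. The public text does not give the timing, and since the introduction is partly redacted, that silence cannot be held against the plan. This reply stands as a limit on the expected benefit.

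Third, other controls exist: the 2-week monotherapy DLT period, the Cycle 1 entry rules on AST and ALT, each participant's own Day 8 and Day 14 tests, and continuous safety review. These matter, but the entry rules govern a participant's own move to combination, not the start of the next participants.

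Finally, the Cycle 1 sentinel at the first level has the same Day 1 to Day 8 laboratory interval, so changing Cycle 0 alone may look inconsistent. Table 2-3 has no visit between those days, so a test there would need a new one. The proposal goes only as far as the existing visits allow.

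**Conclusion.** The gap is real and follows directly from the two sections: no on-treatment chemistry or LFT result is scheduled for the Cycle 0 sentinel before the others may be dosed, and the first is drawn 2 to 3 days later. This holds at every dose level and rests only on how the 5 days are counted.

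The conclusion is a cheap improvement to a deliberate schedule. A reader might go further and infer that the escalation is unsafe, or that the sentinel goes unmonitored. Neither follows: the window has examinations, ECGs, adverse event review and blood counts, and later controls apply. How many doses others would actually take before the sentinel's Day 8 draw depends on their start dates, which the documents do not give. If they start on or after the sentinel's Day 8, the chemistry has at least been drawn by then. The chance that a Day 3 or Day 4 test would be abnormal cannot be estimated from the documents either. The case rests on a purely laboratory DLT criterion, first-in-human dosing and a very low cost.

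**What to change.** **Table 2-2, sentinel only.** Take the existing Day 4 (±1) predose blood count on Day 3 or Day 4, and add chemistry and LFTs to that draw.

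**Section 5.1.2.1.** State that these local results are reviewed before further participants in that cohort are dosed. If they meet a DLT criterion, or the Grade 2 AST/ALT rule in Section 7.4.1, dosing of the others waits for the Medical Monitor's agreement. Without a stated action the review would add delay but no decision.

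Keep the sentinel's Day 8 and Day 14 tests, since a normal early result does not exclude a later rise. Keep weekly chemistry for everyone else.

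**Cost.** One extra local tube per sentinel, with 7 planned dose levels and more if intermediate levels are added. The sentinel's draw window narrows from 3 days (Days 3 to 5) to 2 (Days 3 and 4). If a result is late, the rest of the cohort may wait briefly. No new visit is needed.

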5.1.2.2 Part 2: Dose-Expansion Cohorts

The purpose of cohort expansion is to gather additional safety, tolerability, preliminary efficacy, PK, and pharmacodynamic information regarding BMS-986242 in combination with nivolumab.

Six disease-restricted populations will be included in the dose-expansion cohort phase. These are melanoma, NSCLC, SCCHN, RCC, BUC, and gastric cancer. PD-(L)1 inhibitors are an approved treatment option for melanoma, NSCLC, SCCHN, RCC, and BUC, and prior treatment may impact preliminary efficacy; thus separate cohorts (PD-(L)1 inhibitor naive or experienced) will be enrolled for these 5 tumor types. Approximately 20 participants will be included in each dose-expansion cohort, for a total of approximately 220 participants in Part 2.

Continuous evaluation of toxicity events in the cohort expansions will be performed throughout enrollment in the expansion cohorts. If, at any time, the aggregate rate of treatment-related toxicities meeting DLT criteria exceeds 33% across all participants treated in cohort expansions, the findings will be discussed and further enrollment may be interrupted. Depending on the nature and grade of the toxicity and after assessing the risk/benefit ratio, a new dose(s) for all cohorts may be initiated at a previously tested lower dose level or at a dose level intermediate to previously tested lower dose levels.

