10.1.2 Dose-expansion Cohort

Dose-expansion cohorts of BMS-986242 administered in combination with nivolumab in 6 disease-restricted populations will be included. These are melanoma, NSCLC, SCCHN, RCC, bladder, and gastric cancer, with separate cohorts based on prior PD-(L)1 exposure in 5 of the tumor types (except gastric cancer). Approximately 20 participants will be included for each dose-expansion cohort, for a total of 220 participants for Part 2. The sample size of 20 participants per dose-expansion cohort is not based on statistical power for comparison but on consideration of the precision of the estimates for ORR proportion. A total of 20 participants are expected to provide a standard error of the estimate of 7% to 11% for ORR proportions between 10% and 50%.

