3 DECISION RULE FOR DOSE ESCALATION AND SIMULATION

Dose escalation recommendations for BMS-986242 monotherapy and in combination with nivolumab will be based on the inference from the Bayesian posterior and the probability that the true DLT rate for each dose lies in 1 of the following categories:

- [0%, 16%) under-dosing
- [16%, 33%) targeted toxicity
- [33%, 100%] excessive toxicity

These boundaries are similar to the toxicity boundaries used by a rule-based design (ie, 3 + 3 design) in that a minimum is set at 16% (about 1 in 6) DLT rate and a maximum at 33% (about 2 in 6) DLT rate. Following the principle of EWOC, dose recommendations for the next cohort will be based on the Bayesian model after DLT information becomes available during the DLT period, accounting for all of the available data from the administered doses, and the candidate doses are the ones fulfilling the overdose criterion that there is less than 25% (for monotherapy) and 35% (for combination therapy) chances of excessive toxicity. Only the candidate doses will be considered for the next cohort. While the Bayesian model will use DLT information from the DLT period only, clinical assessment will take into consideration of the totality of available data including PK/Pharmacodynamics from all treated participants.

The MTD is the highest administered dose not expected to cause DLT in more than 33% of the treated participants during the DLT period. The final recommended MTD/RP2D will be based on the recommendation from the BLRM/BLRM-copula, and on an overall assessment of all available safety, PK/Pharmacodynamic, and efficacy data.

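### The Part 2 toxicity trigger pools all 11 expansion cohorts, so late in accrual it cannot detect one highly toxic cohort; a cohort-level prompt for discussion and a stated counting window are needed

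*Combined protocol and SAP*

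**What the plan says.** Section 5.1.2.2 sets the monitoring: "Continuous evaluation of toxicity events in the cohort expansions will be performed throughout enrollment in the expansion cohorts". The trigger is met if at any time "the aggregate rate of treatment-related toxicities meeting DLT criteria exceeds 33% across all participants treated in cohort expansions". The response is that "the findings will be discussed and further enrollment may be interrupted". After the nature and grade of the toxicity and the risk/benefit have been assessed, "a new dose(s) for all cohorts may be initiated at a previously tested lower dose level" or at an intermediate level.

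On size, Section 10.1.2 states "Approximately 20 participants will be included for each dose-expansion cohort, for a total of 220 participants for Part 2". Section 5.1.2.2 explains the count: besides gastric cancer there are five tumor types, and "separate cohorts (PD-(L)1 inhibitor naive or experienced) will be enrolled for these 5 tumor types".

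The 33% figure matches the upper limit in Appendix 7, Section 3, which classes DLT rates as "16%, 33%) targeted toxicity" and ties the MTD to the DLT period. The operating characteristics in Appendix 7 cover Part 1 only. Section 10.1.2 justifies 20 per cohort by ORR precision alone. For the Part 2 trigger the plan gives no minimum number, look schedule, follow-up window, cohort-level threshold or error rate.

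**The concern.** A single pooled proportion answers one question: is the regimen too toxic on average across Part 2? It does not answer whether it is too toxic in one of the 11 populations. As accrual proceeds, each cohort of 20 shrinks to one eleventh of the denominator, so an excess in one cohort is averaged away. Participants enrolled too recently to have been observed also count as treated, and they dilute the rate further.

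Early on the opposite happens. With no minimum number, one event among the first three participants is 33.3% and meets the trigger.

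At stake is whether the one numerical study-level check in Part 2 would prompt anyone to look at a cohort in trouble. The other oversight (Section 5.1.5, Sections 7.4.2 to 7.4.5) sets no cohort-level rate, and the planned DLT summary in Table 10.3.2-1 is by dose level, not by expansion cohort.

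**Working it through.** **The plan's own figures.** Cohorts: 5 × 2 + 1 = 11, and 11 × 20 = 220. Standard error of ORR, √(p(1−p)/20): 6.7% at 10% and 11.2% at 50%, matching the stated 7% to 11%. The plan states no figure for the trigger.

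**Masking at full accrual.** Events needed: 0.33 × 220 = 72.6, so 73 (73/220 = 33.2%).

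- *One cohort with 20/20 events, the others at 20%.* Expected pooled rate (20 + 0.20 × 200)/220 = 60/220 = 27.3%. To reach 73, the other 200 must contribute 53 (26.5%). P(Bin(200, 0.20) ≥ 53) = 1.6%.
- *One cohort at a true 60%, the others at 20%.* Expected pooled rate (12 + 40)/220 = 23.6%. Convolving Bin(20, 0.60) with Bin(200, 0.20), P(at least 73) = 0.06%.
- *One cohort at 60%, the others at 25%.* Expected (12 + 50)/220 = 28.2%, and P = 5.5%.

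Order of accrual matters. With one cohort at 60%, the others at 20% and randomly mixed enrollment, the rule fires at or after participant 60 in 8% of simulated trials. If the toxic cohort enrolls last, it fires from participant 200 on in 0.06%. Dilution by participants without follow-up is not modelled; it would lower the observed rate further.

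**Early noise.** Exact binomial recursion for P(X/n > 0.33 at any look up to n = 220), one common true rate, outcomes known at each look:

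| True rate | Look after each participant | Every 10 | Every 20 |
|---|---|---|---|
| 10% | 30% | 1% | 0.2% |
| 20% | 60% | 18% | 10% |
| 25% | 75% | 39% | 28% |

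Most of the first column arises at once. Any event in the first three participants fires the rule, with probability 1 − (1 − p)³: 1 − 0.80³ = 49% at a true 20%.

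**A cohort-level prompt.** Prior Beta(0.5, 0.5), so the posterior after x events in n is Beta(x + 0.5, n − x + 0.5). Flag when P(rate > 33%) exceeds 0.90, from n = 10 on. At n = 10, x = 5 gives 0.872 and x = 6 gives 0.961, so the boundary is 6/10. At n = 20, x = 9 gives 0.872 and x = 10 gives 0.944, so it is 10/20. With a look after each participant from 10 to 20:

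| True rate | One cohort flagged | At least one of 11, all at that rate: 1 − (1 − f)¹¹ |
|---|---|---|
| 20% | f = 1.9% | 19% |
| 25% | f = 6.0% | 49% |
| 30% | f = 14.0% | 81% |
| 50% | 74% | – |
| 60% | 93% | – |

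**The case against.** The strongest defence is that this is a prompt, not a stopping rule. Crossing 33% leads to discussion and perhaps a pause, and the protocol claims no error rate for it. Discussing a DLT-type event among the first few participants at a newly selected dose is cheap and arguably desirable. That stands, and it makes early firing a minor cost. A reader might take the 60% and 75% figures as the rule's false-alarm rate. The documents do not support that: they fix no look after every participant, and Section 5.1.5 describes at-least-monthly signal detection and investigator calls. The range by look frequency is the fair statement.

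Pooling also has a rationale. The regimen is common to all cohorts, any dose change would apply to all of them, and cohorts were split because prior PD-(L)1 treatment may affect efficacy. No passage predicts that toxicity will differ between cohorts. This stands too: the masking scenarios are assumptions. They show what the rule would miss, not what is expected.

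Two stronger readings should be resisted. One is that events are counted over the full 104 weeks against a limit set for a DLT window of a few weeks. In the trigger sentence, the phrase about time says when the rate may cross, not how long each participant is counted, and the DLT criteria in Section 7.4.1.1 are headed for the DLT periods. The counting window is unstated, which is an ambiguity and no more. The other is that this is the only quantitative safeguard in Part 2. Participant-level rules for dose modification, delay and discontinuation (Sections 7.4.2 to 7.4.5) contain numerical criteria, and the Medical Surveillance Team could notice a cluster in an open-label study. What remains true is that none of these sets a cohort-level rate.

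**Conclusion.** The concern holds as a masking problem. Followed as written, the numerical trigger has almost no chance of responding to one highly toxic cohort late in accrual: 0.06% at full accrual for a cohort at 60% and 1.6% for 20/20 events, with the others at 20%. This rests on independent events and on the other cohorts running at about 20% or below. It weakens if they run near 25% (5.5% for a cohort at 60%) or if the toxic cohort enrolls first. It concerns the trigger, not the study's whole safety oversight.

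Early noise is real but secondary. Its size depends on a look schedule that the plan does not state, and its consequence is non-binding. The unstated counting window affects both.

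This is a worthwhile, inexpensive improvement to a design choice, not an error that invalidates Part 2. The statistical analysis plan is still to be finalized (Section 10.3) and could carry the operating characteristics.

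**What to change.** Keep the pooled 33% prompt. Then:

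1. **Add a within-cohort prompt for discussion.** For example, from 10 participants on, flag a cohort when the posterior probability that its rate exceeds 33% is above 90% under a Beta(0.5, 0.5) prior (6/10, 10/20). Before 10 participants the pooled prompt still responds to early events.
2. **State the counting window for Part 2.** Calculate both rates on participants who have completed the window or had an event in it.
3. **State the look frequency and publish the operating characteristics** of both prompts.

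The response to a flag stays as Section 5.1.2.2 has it. No dose or patient-management rule changes.

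The cost is a short boundary table and more discussions. Rates of 20%, 25% and 30% all lie inside the plan's own target interval, yet with all 11 cohorts at one of them at least one is flagged about 19%, 49% or 81% of the time. The plan should disclose this. If it is too many, raise the cutoff to 0.95. At 20% and 25% a single cohort is then flagged 0.9% and 3.0% of the time, so the chance of any flag falls to about 9.5% (1 − 0.991¹¹) and 29% (1 − 0.970¹¹). Detection of a cohort at 50% or 60% falls to 60% or 87%. A smaller cost is that events enter the count sooner than event-free participants, so rates run slightly high during fast accrual.
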